Surgical resection of recurrent or progressive tumor for tumor analysis is an optional procedure. In these individuals SGT-53, at a dose of 3.6 mg DNA per infusion, will be administered twice (on days -1 and -3) in the week prior to surgery. Surgical resection is Day 0. 14-21 days post operatively and having recovered from the effects of surgery, the patients will then start cyclical TMZ with

Study Subject Population

The study population is subjects with confirmed glioblastoma or gliosarcoma who have proven tumor recurrence or progression. Study participants must have measurable disease on imaging studies and Eastern Oncology Cooperative Group (ECOG) performance status 0-2 (Karnofsky performance status [KPS] > 60). Tumors amenable to surgical resection is not a requirement.

Study Procedures

After screening, SGT-53 study drug will be administered by iv infusion twice weekly, beginning on Day 1 of a 28 day cycle as described above with Temozolomide administered orally daily on days 9-13 of each cycle at 150mg/m2 (cycle 1), and 200mg/m2 as tolerated from cycle 2 onwards provided the patient meets the criteria for non-hematological toxicity, ANC and platelet counts. . In those patients who have undergone the optional surgical resection, the 1st cycle of SGT-53 and TMZ will commence 14-21 days post operatively and after having recovered from the effects of surgery. Following first infusion of study agent on Day1, participants will be evaluated weekly for a total of at least 12 weeks. At these weekly study visits, participants will have a physical examination, routine chemistry, and complete blood count.

- After screening, SGT-53 will be administered by iv infusion twice during the week prior to surgical resection of the tumor. 14-21 days post operatively and having recovered from the effects of surgery, SGT-53 study drug will be administered by iv infusion twice weekly beginning on Day 1 of a 28 day cycle as described above.
- A sample of the tumor obtained at resection will be employed to assess levels of exogenous wild type (wt) p53 cDNA to validate targeting.

Primary Study Outcome Measures

• To evaluate the 6 month PFS in patients treated with SGT-53 in combination with Temozolomide.

Secondary Study Outcomes

- To assess safety of the combination of SGT-53 and Temozolomide by analysis of adverse experiences, clinical laboratory tests and physical examinations.

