4.6 Study Design

Based on efficacy and overall safety demonstrated in preclinical studies and the first-in-man Phase Ia and Phase Ib study in combination with docetaxel, SynerGene Therapeutics, Inc. proposes to perform a Phase II clinical study of the combination SGT-53 and temozolomide in subjects with confirmed glioblastoma who have proven tumor recurrence or progression. The goals of the proposed clinical study are to determine the anti-tumor activity of the combination

of SGT-53 and temozolomide by RANO and by evaluating the 6 month PFS; PFS and, OS and by evaluating the safety of the combination of SGT-53 and temozolomide.

The goals of the optional surgical resection are to demonstrate the nanoparticle delivery of systemically administered SGT-53 to tumor in GBM patients and to assess induction of apoptosis by SGT-53 in the tumor. Participation in the optional surgical resection will be at the discretion of the subject and investigator.

Based on the pre-clinical intra-tumoral half-life, in Phase Ia SGT-53 was given as a twice-weekly intravenous infusion over 1.5-2 hours, depending on dose level. The time of infusion can be extended in the event of infusion reactions (see Section 9.3.2); however infusion of the study agent must be completed as soon as possible, but no longer than eight hours after dilution in dextrose.

Below is the schedule of treatment:

This is a single arm study wherein SGT-53, at a dose of 3.6 mg DNA per infusion, will be administered. Patients will receive SGT-53 every 3rd or 4th day in 28 day cycles (total of 6 infusions) starting on Day 1 (cycle 1), Day 29 (cycle2) and Day 57 (cycle 3). Temozolomide will be administered by mouth daily on days 9-13 of each cycle at 150mg/m2 (cycle 1), and 200mg/m2 as tolerated for cycle 2 and beyond provided the patient meets the criteria for non-hematological toxicity, ANC and platelet counts (as given in 9.7.2). In those patients who had a surgical resection, the 1st cycle of SGT-53 and TMZ will start 14-21 days post operatively and having recovered from the effects of surgery.

Patients who are responding to treatment (at least stable disease by RANO) may receive three additional cycle of SGT-53/Temozolomide therapy at investigator's discretion. Alternatively, they may continue on Temozolomide alone at investigator's discretion.

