If optional surgical resection will be performed, SGT-53 will be administered on day -3 and day -1 prior to surgery. Surgical resection of recurrent or progressive tumor is Day 0. 14-21 days post operatively and having recovered from the effects of surgery the patients will then start cyclical TMZ with SGT as described above. A maximum of 6 patients will be have this optional testing. Once the presence of exogenous wtp53 from SGT-53 is demonstrated in the resected tumor of 3 patients, the option for surgical resection for tumor analysis will no longer be offered.

4.6.1. Dose Selection:

In the Phase 1a study of SGT-53 as a single agent the nanocomplex was administered twice weekly for five consecutive weeks. No patient received more than 10 infusions in a single cycle. Two cycles of 10 infusions were administered to one patient.

In various clinical trials Temozolomide has been administered daily for 5 days in one 28 day period. To optimize effectiveness of the potential chemosensitization of SGT53, SGT53

treatment will be given three times prior to the start of temozolomide treatment. Pre-clinical studies have shown that the wtp53 tumor suppressor gene delivered by the SGT-53 nanoparticle functions to sensitize tumors to the chemotherapeutic agent, making them more responsive to the drug. Thus, it is critical that p53 be expressed when temozolomide is administered in order to have the benefit of the SGT-53. Using the proposed schedules, SGT-53 is being expressed at the start of temozolomide treatment. For patients who undergo optional surgical resection for tumor analysis, two doses of SGT-53 will be administered in the week prior to surgical resection of the tumor to demonstrate the presence of exogenous wtp53 in the tumor to validate SGT-53 crossing the BBB and targeting the tumor.

4.6.2. Treatment Duration:

Patients will receive a total of 3 cycles of TMZ in combination with SGT. Patients who are responding to treatment (at least stable disease by RANO) may receive three additional cycles of SGT-53/Temozolomide therapy at investigator's discretion. Alternatively, they may continue on Temozolomide alone at investigator's discretion.

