			after the first event, if recurs
			reduce to 100 mg/m ² etc
			If recurs at lowest dose of TMZ
			(100 mg/m ² or less), withdraw
			from study. If at any time it does
			not resolve within 14 days,
Tr1 1	ZUNA	<75 000 to	withdraw from study.
Thrombo-	<lln td="" to<=""><75,000 to	Grade 3: <50,000 to 25,000/mm³	</lln>	<75,000 to	Grade 3: <50,000 to 25,000/mm ³
cytopenia	$75,000/\text{mm}^3$	50,000/mm ³	Grade 4: <25,000/mm ³
	Proceed at	Proceed at	If resolves to grade ≤ 2 within 14 days, rechallenge at same dose of
	current dose	current dose	SGT-53, and reduce dose of TMZ
	current dosc	current dosc	in increments after each event
			according to Table 9.7.2b below,
			i.e.in Cycle 1 reduce to 100
			mg/m^2 after the first event, in
			Cycle 2 reduce to 150 mg/m ² after
			the first event, if recurs reduce to
			100 mg/m ² etc
			If recurs at lowest dose of TMZ
			(100 mg/m ² or less), withdraw
			` '
			not resolve within 14 days,
			withdraw from study.
			(100 mg/m ² or less), withdraw from study. If at any time it does not resolve within 14 days,

Table 9.7.2.b Dose de-escalation for TMZ:

Treatment Cycle	Agent	Schedule	Level	Level	Level
			0 (Target Dose)	-1	-2
Cycle 1	TMZ	Days 9-13	150 mg/m^2	100mg/m^2	
Cycle 2 onwards		Days 9-13	200 mg/m ²	150 mg/m ²	100 mg/m^2

In the event of grade III or higher toxicity associated with TMZ after cycle 1, treatment will be interrupted and patient monitored for resolution of toxicity, with subsequent reinitiation of treatment. TMZ dosing will resume after complete resolution of toxicities to Grade II or less.

The dose of Temozolomide will only be escalated to 200 mg/m2 if the patient meets the following criteria: If the CTC nonhematologic toxicity for Cycle 1 is \leq Grade 2 (except for alopecia, nausea, and vomiting, diarrhea, or fever, chills or hypotension which respond promptly to treatment and lasts less than 24 hours), absolute neutrophil count (ANC) is \geq 1,500/mm³, and the platelet count is \geq 100,000/mm³. The dose remains at 200 mg/m2 per day for the first 5 days of each subsequent cycle except if toxicity occurs. If the dose was not escalated at Cycle 2, escalation should not be done in subsequent cycles.

If more than a 2 week delay is required to meet hematologic parameters for treatment, the patient must be removed from study and replaced.

9.7.3. Dose de-escalation for SGT-53:

Permitted dose modifications for SGT-53

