10.2. Evaluation During Study

The starting dose of SGT-53 will be 3.6 mg of DNA. If necessary, dose de-escalation for SGT-53 will proceed according to the dose de-escalation scheme in Table 9.7.3 above. Assessment of DLTs will be made based on the first cycle (4 weeks of treatment). At the end of the first cycle, if no DLT are observed, additional patients may be enrolled and treated simultaneously. If the first patient experiences a DLT in the first cycle (4 weeks), then only one additional patient will be enrolled and evaluated for DLT. If the second patient does not experience DLT in the first cycle (4 weeks), then additional patients may be enrolled simultaneously.

10.2.1. Patients with Optional Surgical Resection for Tumor Analysis:

Beginning 5 days prior to scheduled surgical resection of their recurrent glioblastoma, patients will initiate 3.6mg DNA dosing/infusion with SGT. Dosing will continue through the day before surgery.

• One portion of the surgical section will be saline rinsed and flash frozen for measurement of exogenous wt p53 in tumor tissue, one portion will be immediately formalin-fixed for evaluation of PD biomarkers of activity of SGT-53 including but not limited to Annexin V and TUNEL staining. In addition, one portion of fresh tissue will be used for flow cytometry and/or immunohistochemistry analysis to determine the level of apoptosis in Cancer Stem Cells (CSC) and bulk tumor cells. Any remaining tumor tissue from an earlier procedure will be collected and stored in a research tissue bank at Georgetown University or the clinical site.

Following surgery, an MRI scan should be done no later than 72 hours from the time of surgery.

Following recovery from surgical resection (POD ~14-21), patients will restart SGT-53 and TMZ on the morning of Cycle 1 Day 1 (C1D1). Each cycle will consist of 28 days. Patients will return to the clinic for twice weekly (every 3rd or 4th day) infusions of SGT-53 for three weeks (see treatment schedule diagram in section 9.1.1). Temozolomide will be taken daily by mouth daily on days 9-13 of each cycle. During week 4 of each cycle the patient will not receive any treatments. Patients will return to the clinic on Day 29 (C2D1) and Day 57 (C3D1) for evaluation. If the drug has been well tolerated, continued dosing will be permitted even if they appear to be progressing.

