Patients will be monitored for response and disease progression with MRI brain scans every 2 cycles (8 weeks) and/or at the end of cycle 3, or earlier if progressive disease is suspected.

All patients who participate in this study will continue treatment with SGT-53 and TMZ after surgery. The following conditions should be satisfied before initiation of treatment with SGT:

- 1) They have recovered from the effects of surgery including adequate wound healing.
- 2) A brain MRI should be done no later than 72 hours in the immediate post-operative period to best assess the extent of residual measurable disease post-operatively.
- 3) The patient has followed the study requirements for birth control and pregnancy testing since the initial pre-operative doses of SGT and TMZ.
- 4) Post-operatively, patients must have adequate bone marrow function (absolute neutrophil count > 1,500/ μ L and platelet count of >100,000/ μ L), normal coagulation profile (PT/PTT), adequate liver function (SGPT, SGOT, and alkaline phosphatase <2.5 times upper limit of normal and bilirubin < 1.5 X upper limit of normal), adequate renal function (BUN or creatinine <1.5 times upper limit of institutional normal within 7 days prior to starting therapy.
- 5) The patient continues to meet all the eligibility criteria of the study outlined above.

10.2.2. Patients Not undergoing Surgical Resection:

Patients who have had surgery for recurrent glioblastoma will follow the guidelines listed above for patients with optional surgical resection for tumor analysis.

If no surgery has been performed, patients will start SGT-53 and TMZ on the morning of Cycle 1 Day 1 (C1D1). Each cycle will consist of 28 days. Patients will return to the clinic for twice weekly (every 3rd or 4th day) infusions of SGT-53 for three weeks (see treatment schedule diagram in section 9.1.1). Temozolomide will be taken daily by mouth daily on days 9-13 of each cycle. During week 4 of each cycle the patient will not

receive any treatments. Patients will return to the clinic on Day 29 (C2D1) and Day 57 (C3D1) for evaluation. If the drug has been well tolerated continued dosing will be permitted even if they appear to be progressing.

Patients will be monitored for response and disease progression with MRI brain scans every 2 cycles (8 weeks) and/or at the end of cycle 3 or earlier if progressive disease is suspected.

10.2.3. All Patients:

Evaluations done at each clinic visit are detailed in Section 18.1.

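### Section 9.7.2 puts 200 mg/m2 temozolomide on the first five days of later cycles, but its own table and every other place that names the days give days 9-13

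*Combined protocol and SAP*

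**What the plan says.** Section 9.7.2 sets the toxicity, neutrophil and platelet conditions for raising TMZ from 150 to 200 mg/m2 after cycle 1. It then says: "The dose remains at 200 mg/m2 per day for the first 5 days of each subsequent cycle except if toxicity occurs". Sections 5 and 9 define a cycle as 28 days beginning with an SGT-53 infusion on day 1, so the first five days of a cycle are days 1-5.

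The other statements of the TMZ days are:

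- **Table 9.7.2.b**, just above that sentence: its schedule column gives days 9-13 in the row for cycle 1 and in the row for cycle 2 onwards.
- **Section 4.6**: TMZ is given "on days 9-13 of each cycle at 150mg/m2 (cycle 1), and 200mg/m2 as tolerated for cycle 2 and beyond".
- **Synopsis (section 3)**: "Temozolomide administered orally daily on days 9-13 of each cycle at 150mg/m2 (cycle 1), and 200mg/m2 as tolerated from cycle 2 onwards".
- **Sections 5 and 9**: the day-by-day treatment lists put TMZ on days 9-13.
- **Sections 10.2.1 and 10.2.2**: "Temozolomide will be taken daily by mouth daily on days 9-13 of each cycle".
- **Calendars in 18.1.1 and 18.1.2**: TMZ is marked on D9 to D13 in cycles 1, 2 and 3.

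Section 9.1.1 gives five days of TMZ per cycle without naming them. Section 4.6.1 gives the reason for the timing: SGT-53 "treatment will be given three times prior to the start of temozolomide treatment".

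**The concern.** One section states two TMZ schedules that have no day in common, and no sentence says which governs. The sentence is part of an operative dosing rule for a cytotoxic drug. It stands in the paragraph to which sections 4.6, 5 and 9 refer for the conditions for going to 200 mg/m2. The calendars stop at cycle 3, so for the optional cycles 4-6 a site has only the text and Table 9.7.2.b.

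What is at stake is the order of the two drugs. The rationale in 4.6.1 is that SGT-53 sensitises the tumour and that p53 should be expressed when TMZ is given. TMZ from day 1 would reverse the intended sequence within the cycle and would shorten one gap between TMZ courses.

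**Working it through.** The plan gives no figure to reproduce, so this is a comparison of schedules with simple day counts. The counts assume no dose delays and apply only to a patient escalated to 200 mg/m2 whose site follows the sentence literally.

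**Inputs**

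- Cycle length: 28 days (sections 5 and 9).
- SGT-53 infusions: days 1, 4, 8, 11, 15 and 18 of each cycle (sections 5 and 9).
- Intended TMZ days: 9-13 (Table 9.7.2.b and the places listed above).
- Literal TMZ days from the 9.7.2 sentence: 1-5.

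**1. Overlap.** The sets {1, 2, 3, 4, 5} and {9, 10, 11, 12, 13} have 0 of 5 days in common. The phrase cannot mean the first five TMZ days, because a cycle has only five.

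**2. TMZ start days.** Study day = 28 x (cycle - 1) + cycle day. The word for later cycles could mean cycle 2 onward or cycle 3 onward, so both are shown.

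| Reading | Cycle 1 start | Cycle 2 start | Cycle 3 start | Intervals |
|---|---|---|---|---|
| Days 9-13 throughout | 9 | 28 + 9 = 37 | 56 + 9 = 65 | 28, 28 |
| Days 1-5 from cycle 2 | 9 | 28 + 1 = 29 | 56 + 1 = 57 | 20, 28 |
| Days 1-5 from cycle 3 | 9 | 37 | 57 | 28, 20 |

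Under either literal reading exactly one interval shortens, from 28 to 20 days. Of the three planned cycles, 2 or 1 would be given on the wrong days.

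**3. TMZ-free days at the changeover (reading from cycle 2).** The first course ends on day 13, so the first free day is 14. Intended: 37 - 14 = 23 days. Literal: 29 - 14 = 15 days.

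**4. SGT-53 before TMZ within the cycle.** Before day 9 there are 3 infusions (days 1, 4 and 8). Before day 1 there are 0.

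**5. Most recent SGT-53 infusion on an earlier day.** Intended: 9 - 8 = 1 day. Literal: the last infusion is day 18 of the previous cycle, so 29 - 18 = 11 days. Under the literal reading, infusions would also fall on days 1 and 4, during the TMZ course itself.

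**6. Dose per cycle.** 5 x 200 = 1000 mg/m2 under both readings.

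**Which schedule is intended.** Days 9-13 fit three infusions followed by TMZ, as 4.6.1 describes; days 1-5 do not. The day-by-day lists and calendars agree on days 9-13. The 9.7.2 sentence is therefore most likely a drafting error.

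**The case against.** The strongest reply is that the document already settles the question. The 9.7.2 sentence is about dose level, that is, whether 200 mg/m2 is kept after escalation. The days are set by Table 9.7.2.b in the same section and repeated in the treatment lists and calendars. Sections 4.6, 5 and 9 refer to 9.7.2 for toxicity and blood-count criteria, not for days, and each names days 9-13 alongside the pointer. This stands: a reader arrives with the right days, and misdosing is unlikely. It lowers the weight of the point but does not make the sentence correct.

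A reader might also infer more than the documents support:

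- **That 4.6.1 expressly requires three infusions before TMZ in every cycle.** It does not say in each cycle, and cycle 1 TMZ would still start on day 9. The per-cycle reading is reasonable, since the same section wants p53 expressed when TMZ is given, but it is an inference.
- **That all patients are exposed.** The sentence covers only patients escalated to 200 mg/m2. Those kept at 150 mg/m2 are outside it.
- **That 10.2.1 and 10.2.2 contain a second contradiction.** Both speak of starting or restarting SGT-53 and TMZ on the morning of cycle 1 day 1. That reads naturally as the start of the combined regimen, and the same paragraph then gives days 9-13.
- **That a 20-day interval shows a bone-marrow hazard.** Section 7.1 reports median nadirs at 26 days (platelets) and 28 days (neutrophils), but in refractory anaplastic astrocytoma and without saying from which day they count. The count criteria for escalation would still apply.

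**Conclusion.** The inconsistency is real and the sentence is wrong as written: in 9.7.2, TMZ for escalated patients is put on days that conflict with Table 9.7.2.b and with every other place that names the days. It is minor. Followed literally, and with no dose delays, it would mean 0 instead of 3 SGT-53 infusions before TMZ within the affected cycle and one TMZ interval of 20 instead of 28 days, with the dose per cycle unchanged. The significance of the infusion count rests on reading 4.6.1 cycle by cycle.

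The documents do not show that any site would dose this way. Nor do they support a claim that the trial's conclusions are at risk: sample size, alpha, power, PFS6 and the Simon decision rule do not depend on this sentence.

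**What to change.** In section 9.7.2, change the timing phrase in the sentence on keeping the 200 mg/m2 dose to: on days 9-13 of each subsequent cycle. It then matches Table 9.7.2.b.

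The cost is one phrase in the next amendment, with no change to visits, dose, sample size or analysis. Rewording 10.2.1 and 10.2.2, so that SGT-53 starts on cycle 1 day 1 and TMZ on day 9, is optional tidying and not part of this point.
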